### **PROTOCOL**

### 1. AIMS 1-3 COMMON APPROACH ELEMENTS

This project's *overall objective* is to develop a broadly applicable method to assess extracellular volume (ECV) and guide precise ultrafiltration to minimize mortality risk factors in maintenance hemodialysis (HD) patients. *Our central hypothesis* is that prospectively prescribing ultrafiltration based on intradialytic blood pressure slopes (IBPS) from recent treatments will be superior to standard care at reducing ambulatory blood pressure and ECV without increasing risk for intradialytic hypotension.

[figure not shown]
To test this, we will conduct an un-blinded randomized clinical trial with an embedded cross sectional study in the baseline period of the trial:

In **Aim 1**, we will implement a cross sectional study using baseline measurements from our clinical trial. We aim to establish the mean IBPS from the prior 2 weeks as a validated clinical metric for assessing ECV compared to bioimpedance spectroscopy analysis (BIA) that can be used in nearly all HD patients.

In **Aim 2**, we will conduct a randomized clinical trial comparing ultrafiltration prescriptions based on IBPS to standard care prescriptions driven by clinical determination of the individual treating nephrologist. We will establish that the IBPS guided approach more effectively modifies two primary mortality risk factors in HD patients: ambulatory blood pressure and ECV excess. We will also assess the mechanistic effect of our intervention by simultaneously measuring total peripheral resistance and cardiac index at baseline and end.

In **Aim 3**, we will analyze data from the trial in Aim 2 to determine if IBPS guided therapy is as safe as standard care by comparing the incidence of intradialytic hypotension and the intradialytic systolic blood pressure nadir.

**1. A RESEARCH DESIGN:** The overall design is a randomized clinical trial (**Figure 1**). An initial analysis of baseline measurements for this trial will comprise the data for Aim 1. Additional subjects who are eligible, but not interested in participating in the whole duration of the clinical trial, may participate in Aim 1 only by getting one set of measurements. Aims 2 and 3 will involve the comparison of outcomes between two assigned groups from beginning to end of the trial.

Patient Population: We will utilize consecutive sampling to identify patients that are eligible for our study. There are approximately 500 prevalent patients in the 3 UT-Southwestern affiliated hemodialysis units at any point in time. We have contacted each individual UTSW nephrologist and obtained permission to review medical records to identify patients that meet the inclusion and exclusion criteria. Inclusion criteria are age >18 years and the presence of hypertension. We will define hypertension as a mean systolic blood pressure greater than 140 mmHg pre-dialysis or greater than 130 mmHg post-dialysis over a 2-week screening period. The pre dialysis blood pressures, post dialysis blood pressures, the lowest blood pressures, and all intradialytic blood pressure measurements are typically obtained every 30 minutes during treatment are electronically stored in the patients DaVita medical records. Exclusion criteria are in **Table 1.** 

Table 1: Exclusion Criteria for Aims 1-3			
Exclusi	on Criteria	Justification	
For Aim	าร 1-3		
1.	Hemodialysis Vintage <1 month	Patients that are newly started on hemodialysis do not have a dry weight that is firmly established.	
2.	Pregnancy	The patient will need specialized fluid removal goals beyond the parameters of our study to optimize outcome of the pregnancy	
3.	Nadir Systolic Blood Pressure <95 mmHg during screening	This defines patients at increased risk for mortality and highest risk for complications with additional fluid removal during dialysis. This is frequently associated with ECV-independent blood pressure during dialysis including related to advanced heart failure or autonomic neuropathy	
4.	Pre or Post Dialysis Systolic Blood Pressure >180 mmHg	This threshold identifies high risk patients who may need more aggressive pharmacologic therapy which will be left to the discretion of the patient's nephrologist.	
5.	Decrease in Systolic Blood pressure >60 mmHg from pre to post dialysis	Further increases in ultrafiltration would be increase further risk for hemodynamic instability	
6.	Ultrafiltration Rate >13 mL/hr/kg	In observational studies, this rate is associated with increased mortality; faster ultrafiltration may put patient at risk for increased morbidity or mortality	
7.	Peridialytic Midodrine Use	This can acutely influence intradialytic blood pressure in an ECV-independent way. Midodrine is used to treat intradialytic hypotension and is frequently used in patients with autonomic neuropathy	
8.	Intradialytic Clonidine Use	This can acutely influence intradialytic blood pressure in an ECV-independent way. This is used to treat severe hypertension during dialysis, and these patients frequently have ECV-independent etiology of hypertension, including possible medication non-adherence	
9.	Documented Antihypertensive Medication Non-adherence	This can acutely influence intradialytic blood pressure in an ECV-independent way.	
Aim 1 C			
10.	Amputated Extremity (excluding fingers, toes, hands, or feet)	Bioimpedance measurements of extracellular water are less accurate if all 4 major limbs are not present.	
11.	Presence of cardiac defibrillator, pacemaker	The current from the bioimpedance electrodes may interfere with the function of these devices	
12.	Presence of metal prostheses	Bioimpedance measurements are less accurate if implanted metal is present	

Eligible subjects agreeing to participate in all aims will be assigned to one of two study groups based on computer-generated randomization stratified by gender: IBPS-based management or Standard of Care (detailed in Aim 2). The presence of contraindications to BIA (see Table 1, #10-12) would not exclude a subject from participating in Aims 2 and 3. Such subjects would complete all study procedures except the BIA and NICOM. The outcomes of Aims 2 and 3 (ambulatory blood pressure and intradialytic hypotension) would still be ascertained. Eligible subjects not willing to undergo randomization into a 16 week trial (Aims 2-3) may participate in the BIA and measurements in Aim 1 only.

In short subjects may participate in Aim 1 only, Aims 2 and 3 only, or all Aims based on individual exclusion criteria and preference. We have successfully recruited more than 125 HD patients over the past several years for various prospective research studies and continue to maintain support from DaVita dialysis units (see Letters of Support).

Study Procedures: All procedures will be conducted by authorized personnel from the UT Southwestern research team consisting of the principal investigator and research nurses/coordinators.

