Impedance Cardiography: We will use bioreactance (Cheetah Non-Invasive Cardiac Output Monitor: NICOM) to obtain measurements of cardiac output (and index) and systolic blood pressure, from which total peripheral resistance (and index) will be calculated. This non-invasive procedure involves detection of intrabeat changes in voltage phase shifts following the application of electric current. The phase shift reflects the change in thoracic fluid volume with each heartbeat. Our device has been validated for measuring cardiac output in intensive care patients, patients with congestive heart failure and HD patients[6-8].

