## 2. SPECIFIC APPROACH BY AIM

AIM 1: The premise for this aim is that there is a need to develop widely-available, easilyimplementable method for accurate assessment of ECV in HD patients. The objective of this aim is to establish the association between ECV excess and IBPS from multiple treatments in hypertensive HD patients. We will test the working hypothesis that when measuring blood pressure every 30 minutes over 6 treatments, there will be a positive correlation between the mean systolic IBPS and the ECV/body weight measured with BIA in a cohort of 66 hypertensive HD patients. We have calculated the IBPS from a single treatment from 49 hypertensive HD patients in a more heterogeneous cohort who also have pre and post-HD BIA measurements. The median slope was -3.36 mmHg/hour (interquartile range -9 mmHg/hr, +3.5 mmHg/hour). There is a positive correlation between the IBPS and the ratio of ECV/body weight measured after HD (Pearson correlation coefficient 0.4, p=0.008). The post-HD correlation was 0.5 in men (n=32. p=0.01), but was 0.3 in the smaller group of women (n=17, p=0.2). It is necessary to demonstrate that the overall relationship between IBPS and ECV/body weight 1) persists when evaluating IBPS from multiple recent HD treatments and 2) is stronger in a more homogeneous cohort of HD patients without the extremely high or low intradialytic blood pressures that are more likely related to comorbid medical diseases than changes in ECV. It is also necessary to better define the association of this relationship with gender in a larger number of subjects with more equal distribution of men and women.

**RESEARCH DESIGN AIM 1:** We will use a cross sectional study design to determine the association between systolic IBPS and measurements of post-HD ECV/body weight using BIA in hypertensive HD patients. Limitations of BIA include that it cannot be used in patients with amputations or implanted metal prostheses due to inaccurate measurements. It cannot be used in pregnant individuals or those with cardiac defibrillators or pacemakers due to safety concerns. For this reason, additional exclusion criteria unique to this aim will be patients with 1) amputations of major extremity, 2) cardiac defibrillator or pacemaker, or 3) implanted metallic device (see Exclusion Criteria #10-12 above).

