### **Statistical Analysis Plan and Power Calculation for Sample Size (Aim 2)**

The primary outcome of this aim will be the ambulatory systolic blood pressure from baseline to 16 weeks. Secondary endpoints include ECV/body weight and total peripheral resistance, from baseline to 16 weeks. We will use the two-sample t test to perform the unconditional comparison of the difference in endpoints over time between treatment and control groups. For conditional comparison, we will use the linear mixed effect model to estimate the fixed effect of the treatment group indicator, while adjusting for the fixed effects from baseline variables and time and the random effect within the same patient. We determined our sample size based on known effects of intense ultrafiltration on ambulatory blood pressure reduction. In the DRIP trial[10], systolic blood pressure decreased by 13.9 mmHg in the intense ultrafiltration group and 6.9 mmHg in the standard group (95% CI -12.2 − 1 mmHg) after 8 weeks. We expect a more modest decrease in systolic blood pressure due to our less aggressive approach per treatment. Assuming a standard deviation for the ambulatory systolic blood pressure change of 6 mmHg (this was approximately 2.7 mmHg in DRIP and our study will have a smaller sample size), we will be able to show with 90% power and an alpha of 0.05, that a between group difference ≥2.7 mmHg will occur. If the normality assumption indeed holds in our observed data, this would require 14 subjects per arm, but we will recruit 30 subjects per arm to facilitate simple normality check such as the Q-Q plot. Assuming a 25% dropout rate, we will aim to recruit 74 subjects (37 in each group).

With our sample size (n=74), we will have 85% power to detect a 0.025 difference in the change between groups after 16 weeks in ECV/body weight. This clinically significant difference is consistent with the difference in post-HD ECV/body weight we found in patients with intradialytic hypertension and HD controls [13]. Based on our prior experiences recruiting HD patients for clinical research, we expect that we will be able to enroll 1-2 patients each month (18 patients each year including excluding dropouts).

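### Subjects with a major limb amputation are denied the NICOM measurement for a reason that applies only to bioimpedance, so they add nothing to the total peripheral resistance endpoint

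*Combined protocol and SAP*

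**What the plan says.** Section 1 lets subjects who cannot have BIA enter the randomized trial: "The presence of contraindications to BIA (see Table 1, #10-12) would not exclude a subject from participating in Aims 2 and 3". It then lists what they miss: "Such subjects would complete all study procedures except the BIA and NICOM".

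Table 1 gives one reason for each of the three criteria:

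- Criterion 10, amputated extremity (loss of fingers, toes, hands or feet does not count): "Bioimpedance measurements of extracellular water are less accurate if all 4 major limbs are not present".
- Criterion 11, defibrillator or pacemaker: "The current from the bioimpedance electrodes may interfere with the function of these devices".
- Criterion 12, metal prostheses: "Bioimpedance measurements are less accurate if implanted metal is present".

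The Aim 1 text in section 2 repeats the amputation and metal reasons, again for BIA alone: "Limitations of BIA include that it cannot be used in patients with amputations or implanted metal prostheses due to inaccurate measurements".

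The Impedance Cardiography paragraph under Baseline Information says that NICOM applies an electric current and reads phase shifts. It describes the signal thus: "The phase shift reflects the change in thoracic fluid volume with each heartbeat".

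The Aim 2 analysis plan makes resistance a secondary endpoint: "Secondary endpoints include ECV/body weight and total peripheral resistance, from baseline to 16 weeks". The Aim 2 outcomes section schedules NICOM at weeks 0, 8 and 16 for eligible subjects. It acknowledges that some subjects will not have NICOM, but does not say why.

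**The concern.** A restriction argued for one instrument has been applied to a second. A missing limb undermines a whole-body estimate of extracellular water. The protocol does not say that it undermines a beat-to-beat signal from the chest.

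Reduced peripheral resistance is the third part of the Aim 2 working hypothesis, and resistance is the measure by which the trial proposes to explain its blood pressure effect. The section on potential problems in Aim 2 says that leaving out subjects with amputations or cardiac devices would hurt both sample size and generalizability. The trial therefore takes them in, but those with an amputation are left out of a stated secondary endpoint for no reason that applies to it. The blood pressure result and the resistance result then describe somewhat different populations, and the resistance result rests on fewer subjects than it need do.

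**Working it through.** **1. Does each stated reason reach NICOM?** The plan gives no figure for this point, so the first step is a comparison of texts.

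| Criterion | Stated reason | Carries over to NICOM on the protocol's own description? |
|---|---|---|
| 10, amputation | Accuracy of bioimpedance extracellular water without all limbs | No. The Aim 1 study procedures call BIA whole body; NICOM is described as thoracic |
| 11, cardiac device | Interference from applied current | It can. NICOM also applies current |
| 12, metal | Accuracy of bioimpedance measurements generally | Undetermined. NICOM is presented as impedance cardiography, and the documents do not say whether or where metal disturbs it |

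Only criterion 10 is left with no reason that could apply to NICOM.

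**2. Does the endpoint need BIA in the same subject?** No. The Aim 2 analysis plan compares the change in total peripheral resistance between arms. Resistance is calculated from NICOM cardiac output and blood pressure, so a subject without BIA can still contribute.

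**3. Is the between-arm comparison biased?** No. Amputation status is a baseline condition, settled before randomization and handled identically in both arms. What is lost is information and coverage.

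**4. How much precision is lost?** The inputs from the Aim 2 analysis plan are 74 subjects, 37 per arm. The share f with an amputation and neither of the other two conditions is not in the documents; the Aim 1 power section says only that most of the 74 will have BIA. I therefore assume f from 5% to 20%.

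The standard error is proportional to 1/√n, so losing a share f multiplies it by 1/√(1 − f).

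The plan states no power for resistance. For illustration, take the standardized difference that has 85% power at 37 per arm (two-sided alpha 0.05, normal approximation):

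d = (1.960 + 1.036) × √(2/37) = 0.697 SD

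With a share f missing, power = Φ(2.996 × √(1 − f) − 1.960).

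| Assumed f | Subjects of 74 | Standard error multiplied by | Illustrative power |
|---|---|---|---|
| 0% | 0 | 1.000 | 85.0% |
| 5% | 3.7 | 1.026 | 83.2% |
| 10% | 7.4 | 1.054 | 81.1% |
| 20% | 14.8 | 1.118 | 76.4% |

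These figures are before dropout. The planned 25% dropout lowers n in every row alike if it is unrelated to amputation, so the multipliers do not change.

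**The case against.** The case for leaving the text alone has four parts.

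**The exclusion looks deliberate.** Section 1 and the Aim 2 outcomes section agree that some subjects will have neither measurement, so there is no contradiction to repair. A missing reason also does not prove that none exists. This stands as far as it goes: the point is an unsupported restriction, not an inconsistency, and a device-specific reason, if the sponsor has one, would answer it.

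**The mechanism question needs both instruments.** The section on potential problems in Aim 2 describes learning how gradual changes in extracellular volume affect resistance and cardiac output. That calls for BIA and NICOM in the same person, and a subject with an amputation cannot supply both. This stands for any analysis linking the two measures. It does not answer the separate between-arm comparison of resistance, which is the listed secondary endpoint.

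**Indexing is awkward after amputation.** The Aim 2 outcomes section refers to the resistance index, and an index scaled to body surface area could be wrong when a limb is missing. This is a fair caution about the index. The analysis plan, however, names resistance without indexing, and the Impedance Cardiography paragraph provides for both.

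**The size is assumed and modest.** This stands in full.

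A reader might go further and infer that the mechanistic endpoint is thrown away needlessly and selectively. The documents do not support that:

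- Resistance is still measured in every eligible subject at three time points; only one subgroup's data go uncollected.
- For metal prostheses, needlessness is not shown. The written reason is broad enough that it may reach NICOM, and a rule based on where the metal lies would need device information that the documents lack.
- The selection is on a baseline condition common to both arms, so it narrows the population without distorting the treatment effect.

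**Conclusion.** The point holds for criterion 10 only. On the protocol's own descriptions of the two instruments, the reason for withholding BIA after a major amputation does not extend to NICOM, and no NICOM reason appears anywhere in the documents. The consequence is lost precision and narrower coverage for one secondary endpoint. The primary outcome is untouched and the randomized comparison of resistance remains unbiased.

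The size cannot be fixed from the documents. The standard error rises by about 3% to 12% if between 5% and 20% of subjects are affected; below 5% the loss is slight. This is a cheap improvement of modest, unquantified value. It is best settled before enrolment, because a baseline reading that was not taken cannot be recovered.

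**What to change.** - **Section 1, text after Table 1:** say that criterion 10 removes BIA only, and that a subject with an amputation who meets neither criterion 11 nor 12 has NICOM at weeks 0, 8 and 16. If the sponsor has a NICOM-specific reason for criterion 10, state it there instead.
- **Aim 2 outcomes section:** bring the wording on who is excluded from BIA and from NICOM into line.
- **Aim 2 analysis plan:** specify the within-subject change in unindexed total peripheral resistance, which is already the quantity named there, so that body-surface-area error after amputation does not enter. Give the expected number of subjects with resistance data.
- **Criteria 11 and 12:** leave criterion 11 as it is. Keep the NICOM exclusion for criterion 12 unless the sponsor confirms from device information that implanted metal does not affect the reading.

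The cost is a few text edits and some extra non-invasive readings at visits these subjects already attend, with equipment already in use. One side effect needs a sentence in the plan: the resistance and extracellular volume analyses will cover slightly different subsets, so any analysis linking the two should be limited to subjects with both measurements.

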### Baseline Information:

Demographics and Data: Study personnel will conduct in-person interviews to ascertain medical comorbidities. Laboratory data (obtained every 1-4 weeks as part of HD unit protocol) will be obtained from the medical chart.

Intradialytic Blood Pressure Measurements: Subjects will have blood pressure measurements obtained during HD using the HD machine built-in sphygmomanometer. Measurements will be obtained every 30 minutes and more frequently in the event of hemodynamic instability. Measurements will be obtained in the non-access arm and electronically stored in patient records. We will obtain all measurements from the 6 prior treatments and use linear regression to calculate the IBPS.

Ambulatory Blood Pressure Measurement: Immediately after a mid-week HD treatment, a Spacelabs 90207 cuff will be placed on the patient's non-access arm. The first cuff inflation will occur in the HD unit, and the subject will be instructed to wear the cuff for 44 hours until the next HD treatment. The cuff will inflate every 30 minutes from 6 a.m. to 10 p.m. and every hour during the night.

Bioimpedance Spectroscopy Analysis (BIA): Bioimpedance analysis involves state of the art non-invasive measurements of extracellular water volumes in maintenance HD patients as demonstrated by comparison to bromide dilution, the gold standard ECV measurement in humans[1, 2]. Opposition to electrical current in the body is measured as reviewed in detail in Kuhlman[3]. Our device (Impedimed SFB7) calculates compartmental water volumes using Cole-Cole model plots of measured reactance and resistance at varying frequencies and using the Hanai equation[4, 5] accounting for height, weight, and sex. Our device is FDA approved to measure ECV in healthy individuals, and also measures intracellular water volumes which can then be used with ECV to provide measurements of total body water.

Impedance Cardiography: We will use bioreactance (Cheetah Non-Invasive Cardiac Output Monitor: NICOM) to obtain measurements of cardiac output (and index) and systolic blood pressure, from which total peripheral resistance (and index) will be calculated. This non-invasive procedure involves detection of intrabeat changes in voltage phase shifts following the application of electric current. The phase shift reflects the change in thoracic fluid volume with each heartbeat. Our device has been validated for measuring cardiac output in intensive care patients, patients with congestive heart failure and HD patients[6-8].

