### POTENTIAL PROBLEMS AND ALTERNATIVES (Aim 1)

Our hypothesis is strongly supported by our preliminary data. In the unlikely event that our experiment proves this invalid, we will have laboratory data and data on total body volume, dialysis prescription, antihypertensive medication use, and ultrafiltration rates to better understand which factors best associate with IBPS in various subgroups. There are some patients whose intradialytic blood pressure would likely be influenced by ECV-independent factors.

This includes 1) patients with very high amounts of acute and chronic ECV who have extremely high ultrafiltration rates (>13 mL/hr/kg) that may induce intravascular volume depletion in the absence of ECV depletion and 2) patients with large decreases in intradialytic blood pressure related to acute loss of total peripheral resistance (patients with diabetes for many years with autonomic neuropathy, patients with sympathetic nervous system dysfunction, patients taking antihypertensive medications during HD). Our exclusion criteria minimize the risk of these factors impacting our study.

3. AIM 2: The premise for this aim is there is a need for individualized fluid management interventions that minimize mortality risk factors in HD patients. The objective of this aim is to demonstrate how IBPS-based ultrafiltration prescriptions affect ambulatory blood pressure and ECV in hypertensive HD patients. We will test the working hypothesis that after 16-weeks, subjects randomized to our algorithm will have larger reductions in 1) ambulatory blood pressure during the interdialytic period, 2) post-HD ECV/body weight (measured with BIA), and 3) peripheral resistance compared to standard care.

Based on our preliminary data showing a relationship between IBPS and ECV/body weight (**Figure 2**), we have developed an algorithm that

assigns ultrafiltration goals based on the IBSP demonstrated over the prior two weeks. With this algorithm detailed in **Table 2 (below)**, subjects with the most negative slopes will have the least aggressive fluid removal while those with positive slopes will have the most aggressive prescriptions.

**RESEARCH DESIGN (Aim 2):** Our design for Aim 2 will be an un-blinded, randomized clinical trial comparing IBPS based fluid management to standard care.

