# **Outcomes** During The Study:

Ambulatory Blood Pressure: The mean ambulatory systolic blood pressure will be the primary dependent variable. We selected this variable because it is the blood pressure metric that best predicts mortality in HD patients[12]. Unlike BIA or NICOM, no subjects that would be excluded from obtaining ambulatory blood pressure measurements in this study. All subjects will have baseline measurements of ambulatory blood pressure at week 0 following a mid-week treatment. It will be repeated at week 16 following a mid-week treatment.

*BIA and NICOM:* At baseline (week 0), all eligible subjects will undergo BIA and NICOM for measurements of ECV/body weight (see Aim 1) and total peripheral resistance index before and after a mid-week treatments. The procedures will all be repeated at week 8 and week 16 following a mid-week treatment.

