# **EXPECTED OUTCOMES (Aim 2)**

We expect the IBPS-based ultrafiltration group to have ≥3 mmHg greater reduction in mean ambulatory systolic blood pressure from baseline to 16 weeks than the standard care group. We expect that such differences could be as high as 7 mmHg based on the DRIP trial. Because our algorithm assigns fluid removal objectively and most hypertensive HD patients have ECV excess that is difficult to identify clinically, we expect that subjects assigned to our algorithm will be assigned more fluid removal over the course of the study than those in the standard care group. We expect the outcomes to include improvement in chronic ECV excess as shown by greater reduction in post-HD ECV and ECV/body weight. We expect to also see reduction in post-HD total peripheral resistance. We do expect ambulatory blood pressure to decrease in the standard care group due to patient motivated lifestyle changes while in a clinical trial. However, we expect that the decrease in blood pressure will be of greater magnitude in our IBPS-based ultrafiltration group as specified above. We expect our algorithm will optimize fluid removal and that the change in post-HD ECV/body weight will be ≥0.025 in the IBPS-based ultrafiltration group compared to standard care.

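### Total peripheral resistance, a named secondary endpoint, is to be calculated from systolic rather than mean arterial pressure, which gives wrong levels and can distort the change from baseline

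*Combined protocol and SAP*

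**What the plan says.** The measurement rule is in Baseline Information, under Impedance Cardiography. The bioreactance device (NICOM) will be used to "obtain measurements of cardiac output (and index) and systolic blood pressure, from which total peripheral resistance (and index) will be calculated". No formula follows, and mean arterial pressure is not mentioned anywhere in the documents.

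The quantity carries weight in Aim 2:

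- The common approach section says the study will "assess the mechanistic effect of our intervention by simultaneously measuring total peripheral resistance and cardiac index at baseline and end".
- The opening paragraph of Aim 2 lists, as the last of three hypothesised reductions, "3) peripheral resistance compared to standard care".
- The Aim 2 statistical analysis plan states: "Secondary endpoints include ECV/body weight and total peripheral resistance, from baseline to 16 weeks".
- Expected Outcomes (Aim 2) adds: "We expect to also see reduction in post-HD total peripheral resistance".

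Outcomes During The Study describes the baseline session as providing "measurements of ECV/body weight (see Aim 1) and total peripheral resistance index before and after a mid-week treatments", repeated at weeks 8 and 16. That section names the index, whereas the analysis plan names TPR without the index.

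**The concern.** Peripheral resistance is conventionally mean arterial pressure divided by cardiac output (less central venous pressure where that is not ignored). Systolic pressure divided by cardiac output is a different quantity. It exceeds resistance by a factor that depends on pulse pressure, so it is not resistance on another scale.

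Aim 2 asks whether resistance falls more under the slope-guided prescription than under standard care. If the systolic rule is followed, the answer partly reflects how pulse pressure changed. A fall in systolic pressure alone would look like a larger fall in resistance than occurred, and a fall in diastolic pressure alone would not register. The reported levels would also not be comparable with resistance values computed in the usual way.

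**Working it through.** **Nothing to reproduce.** The documents give no TPR value, formula, standard deviation, effect size or power. The check is therefore a comparison of the two definitions on illustrative values.

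**Inputs.**

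- Systolic pressure (SBP) 130 to 180 mmHg. The lower end is the post-dialysis inclusion threshold and the upper end is the exclusion threshold, both from the eligibility section.
- Diastolic pressure (DBP) 60 to 100 mmHg and cardiac output (CO) of about 5 L/min. These are assumptions; the documents give neither.
- A 7 mmHg fall in SBP for the change examples. This is the upper end of the between-group difference in Expected Outcomes (Aim 2), used here only as an illustrative within-patient change.

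**Formulas.** MAP = DBP + (SBP − DBP)/3, with central venous pressure ignored.

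- As written: 80 × SBP/CO
- Conventional: 80 × MAP/CO

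**Level at 150/80 mmHg, 5 L/min.** MAP = 80 + 70/3 = 103.3.

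- As written: 80 × 150/5 = 2400 dyn·s/cm5
- Conventional: 80 × 103.3/5 = 1653 dyn·s/cm5
- Ratio: 2400/1653 = 1.45, or 45% too high

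**Range of the factor.** Cardiac output cancels, so the ratio is SBP/MAP = 3/(1 + 2 × DBP/SBP). The same ratio applies to the index.

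- Smallest, 130/100: MAP 110, ratio 130/110 = 1.18
- Largest, 180/60: MAP 100, ratio 180/100 = 1.80

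**Change from 150/80 and 5 L/min (2400 as written, 1653 conventional).**

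| Follow-up | CO (L/min) | As written | Conventional | Effect of the systolic rule |
|---|---|---|---|---|
| 143/80 | 5 | 2288 (−4.7%) | 1616 (−2.3%) | overstated |
| 143/76 | 5 | 2288 (−4.7%) | 1573 (−4.8%) | almost none |
| 150/75 | 5 | 2400 (0%) | 1600 (−3.2%) | missed |
| 143/80 | 4.9 | 2335 (−2.7%) | 1649 (−0.3%) | overstated |
| 143/80 | 4.85 | 2359 (−1.7%) | 1666 (+0.8%) | sign reversed |

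The second row is nearly undistorted because DBP/SBP hardly moves: 80/150 = 0.533 and 76/143 = 0.531. The rule misstates the percentage change whenever that ratio changes.

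**When the sign reverses.** For 150/80 to 143/80, the systolic version shows a fall as long as CO falls by less than 1 − 143/150 = 4.7%. The conventional version shows a rise once CO falls by more than 1 − 101/103.3 = 2.3%. Between those two figures they disagree on whether resistance fell.

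**The case against.** **It may be a wording slip.** The sentence describes a device and contains no equation, so a MAP-based value may have been intended. The documents do not settle this. No other passage corrects it, so an analyst following the plan would use systolic pressure.

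**Both arms use the same formula and the analysis compares changes.** This is partly right. The level error matters less for a comparison of changes, and a shared formula does not by itself favour one arm. But the error in the change depends on how pulse pressure moves. The plan expects the arms to differ in fluid removal and systolic pressure, so pulse pressure may move differently too. Whether it will cannot be known from the documents.

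**The examples are chosen.** This is fair. A calculation that holds diastolic pressure fixed shows only overstatement, and other plausible patterns show none or the reverse. No direction of bias is established.

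**A stronger reading that the documents do not support.** A reader might infer that systolic input ties the mechanistic endpoint to the primary outcome and leaves no independent evidence of mechanism. That does not follow, for three reasons.

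- The primary is ambulatory systolic pressure ("The primary outcome of this aim will be the ambulatory systolic blood pressure from baseline to 16 weeks"), taken from a separate cuff for which "the subject will be instructed to wear the cuff for 44 hours until the next HD treatment". The resistance calculation uses pressure from the NICOM session, so the two share a type of pressure but not the data.
- MAP itself contains one third of systolic pressure. In a simulation of six scenarios, the correlation between the change in TPR and the change in ambulatory SBP was 0.21 to 0.56 with systolic input and 0.19 to 0.48 with MAP. The assumptions were SDs of change of 12 mmHg for session SBP, 7 mmHg for DBP, 0.3 to 0.8 L/min for CO and 6 mmHg for ambulatory SBP, an SBP–DBP correlation of 0.3 to 0.8, and a session–ambulatory correlation of 0.5 to 0.7. MAP weakens the link without removing it.
- Cardiac output is measured and is the denominator in either version, and cardiac index is assessed alongside.

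**Conclusion.** The point holds for the definition of this secondary endpoint. The only rule in the plan uses the wrong pressure. On the assumed diastolic range the level is about 1.18 to 1.80 times the conventional value, and 45% too high at 150/80 mmHg. The error in the change has no fixed direction and can alter the sign when cardiac output falls modestly. These sizes rest on assumed diastolic pressures and cardiac output, on the one-third approximation for MAP, and on ignoring central venous pressure.

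The ambulatory systolic primary outcome, the sample size and the stated power are not affected, since none of them uses TPR. The documents support neither a claim that the resistance endpoint duplicates the primary outcome nor a claim that the error favours the intervention.

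**What to change.** 1. Under Impedance Cardiography, replace systolic pressure with mean arterial pressure from the same session and write out the formulas: TPR = 80 × MAP/CO and TPRI = 80 × MAP/CI. State that central venous pressure is ignored.
2. Confirm that diastolic or mean pressure is recorded at the NICOM session. The protocol mentions only systolic pressure there. The exploratory diastolic slope analysis in Aim 1 shows that diastolic pressure is recorded during dialysis, but not that it is captured at this session.
3. Name one quantity, TPR or TPRI, as the endpoint in both Outcomes During The Study and the Aim 2 statistical analysis plan, and refer to the formula there. Apply it at weeks 0, 8 and 16.

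The cost is protocol and SAP wording if the session already stores diastolic or mean pressure. If it does not, one field must be added to the data collected at that session.
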